Pharmacokinetics	
To characterize the pharmacokinetics (PK) profile of naldemedine 1.25 mg, 2.5 mg, and 5 mg and its metabolite (nor-naldemedine) for the PK endpointsPlasma drug concentrations of naldemedine and nor-naldemedine on:
Day 2 immediately before the morning doseDay 3 immediately before the morning dose and 1 hour and 2, 4, 8, and 12 hours after the morning dose before administration of the evening doseDay 4 immediately before the morning dosePK parameters of naldemedine and nor-naldemedine (C_{max}, T_{max}, AUC, CL/F, $MR_{M/U}$, C_{max}, and $MR_{M/U}$, AUC)
Safety	
To compare the safety of naldemedine 1.25 mg, 2.5 mg, and 5 mg and placebo for the safety endpointsIncidence of treatment-emergent adverse events, including those that are serious and those that result in discontinuation of study treatmentProportion of patients with clinically significant changes in clinical laboratory tests, vital signs, and ECGsChange from baseline in pain intensity, as assessed on a Numerical Pain Rating Scale (NPRS)Total dose of intra- and postoperative opioid analgesics in morphine milligram equivalents (MMEs)

AUC = area under the plasma concentration-time curve; CL/F = apparent total clearance estimated according to: $CL/F = Dose/AUC_{0-\infty}$ on Day 3 (for naldemedine only); C_{max} = maximum observed plasma concentration on Day 3; ECGs = electrocardiograms; $MR_{M/U, AUC}$ = metabolic ratio of $AUC_{0-\infty}$ of nor-naldemedine to $AUC_{0-\infty}$ of naldemedine, corrected for molecular weight, defined as $(\text{nor-naldemedine } AUC_{0-\infty})/(\text{naldemedine } AUC_{0-\infty}) \times (\text{naldemedine molecular weight } [570.64])/(\text{nor-naldemedine molecular weight } [516.55])$ (for nor-naldemedine only); $MR_{M/U, C_{max}}$ = metabolic ratio of C_{max} of nor-naldemedine to C_{max} of naldemedine, corrected for molecular weight, defined as $(\text{nor-naldemedine } C_{max})/(\text{naldemedine } C_{max}) \times (\text{naldemedine molecular weight } [570.64])/(\text{nor-naldemedine molecular weight } [516.55])$ (for nor-naldemedine only); T_{max} = time to maximum plasma concentration on Day 3

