## 10.8 Opioid analgesics

Morphine milligram equivalent (MME) (mg) will be calculated as (dose of opioid analgesics) x (conversion factor). The conversion factor by opioid type is shown in Table 6 below; the table will be updated prior to database lock if additional opioid types need to be added.

MMEs will be summarized as continuous variables on each day.

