**Table 6 Conversion Factor**

Opioid Type (Route)	Unit	Conversion Factor
LEVOMETHADONE	mg	8
LEVORPHANOL	mg	7.5
HYDROMORPHONE	mg	4
METHADONE	mg	4
OXYMORPHONE	mg	3
FENTANYL (Topical or Transdermal)	ug/hour	2.4
OXYCODONE	mg	1.5
HYDROCODONE	mg	1
MORPHINE	mg	1
CODEINE	mg	0.15
DIHYDROCODEINE	mg	0.15
FENTANYL (Intravenous, Sublingual or Transmucosal)	ug	0.1
MEPERIDINE	mg	0.1
BUTORPHANOL	mg	0
PENTAZOCINE	mg	0
TAPENTADOL	mg	0
TRAMADOL	mg	0
BUPRENORPHINE	mg	0
SUFENTANIL	mg	0

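### Six opioids in SAP Table 6 carry a conversion factor of 0 with no stated reason, so their doses add nothing to the total-opioid-dose safety endpoint

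*SAP*

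**What the plan says.** Protocol Section 3 (Table 3-1) lists among the safety endpoints "Total dose of intra- and postoperative opioid analgesics in morphine milligram equivalents (MMEs"). Protocol Section 9.4.6 says that opioid doses recorded in the eCRF will be converted to MME with conversion factors and leaves the details to the SAP. It exempts no opioid. Inclusion criterion 4 (Protocol Section 5.1) requires planned primary postoperative pain management with opioids by any route, without restricting the choice of opioid.

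SAP Section 10.8 supplies the details. MME "will be calculated as (dose of opioid analgesics) x (conversion factor"), with the factors in Table 6, and it is summarised as a continuous variable on each day. The zero rows read "BUTORPHANOL mg 0", "PENTAZOCINE mg 0", "TAPENTADOL mg 0", "BUPRENORPHINE mg 0" and "SUFENTANIL mg 0". Tramadol, also in mg, has the same factor of 0. For contrast, one of the two lowest non-zero rows reads "MEPERIDINE mg 0.1". The section allows the table to be updated before database lock, but only to add opioid types that it lacks.

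**The concern.** A factor of 0 does not mean that no factor is available. It enters a recorded opioid dose into the analysis as an observed value of zero, and that zero stays in the daily mean. SAP Section 6.4 says that missing values are not imputed. If the zeros stand for unavailable factors, the table in effect imputes no opioid for those doses.

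The endpoint matters because the test drug is a mu-opioid receptor antagonist. Opioid dose, read together with pain scores, shows whether patients on active treatment need more analgesic. If part of that need is met with one of the six drugs, the MME summary does not register it. The update rule in SAP Section 10.8 does not repair this, because the six drugs are already in the table.

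**Working it through.** The documents state no figure to reproduce. The check is a count of the table followed by the SAP's own formula.

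**Inputs from the documents.** Formula: MME = dose × factor (SAP Section 10.8). I take a day's MME as the sum over all opioids recorded, which the section implies but does not spell out. Factors from Table 6: morphine 1; intravenous fentanyl 0.1 per µg; tramadol 0.

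**Inputs assumed.** Example doses of 30 mg morphine and 200 mg tramadol, used only to exercise the formula. An assumed range of 0.05 to 0.4 for a replacement factor. An assumed share of 5% to 30% of a group receiving only zero-factor drugs. The documents give none of these.

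**Step 1: count.** Table 6 has 19 rows. Six have factor 0 and 19 − 6 = 13 have a non-zero factor.

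**Step 2: single patients under the SAP formula.**

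| Opioids recorded | Calculation | MME |
|---|---|---|
| Tramadol 200 mg only | 200 × 0 | 0 |
| Morphine 30 mg only | 30 × 1 | 30 |
| Morphine 30 mg + tramadol 200 mg | 30 × 1 + 200 × 0 | 30 |
| Intravenous fentanyl 100 µg only | 100 × 0.1 | 10 |

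The first patient cannot be told apart from one who received no opioid. The third cannot be told apart from the second: the dose is under-counted, but the patient is not shown as opioid-free.

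**Step 3: how much the mixed patient loses, over the assumed factor range.**
- Factor 0.05: 30 + 200 × 0.05 = 40 MME, of which the SAP counts 30/40 = 75%.
- Factor 0.4: 30 + 200 × 0.4 = 110 MME, of which the SAP counts 30/110 = 27%.

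**Step 4: group mean.** Let a share q of the group receive only zero-factor drugs, let the rest receive none of them, and let every patient have the same true MME, M. The reported mean is (1 − q) × M. With M = 60:
- q = 5%: 0.95 × 60 = 57, understated by 5%.
- q = 30%: 0.70 × 60 = 42, understated by 30%.
- q = 0: no understatement.

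**Step 5: arm comparison.** With equal true means, 10% exclusive users in one arm and 20% in another would give 0.90M and 0.80M. The second is 1 − 0.80/0.90 = 11% lower, and the difference is spurious. Swapping the shares reverses the sign. Equal shares leave the ratio of means at 1. Nothing in the documents says which case applies.

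**The case against.** The zeros may be deliberate. A sponsor can choose not to convert certain opioids, and whether a given factor is right depends on sources outside these documents. That stands as far as it goes: no individual zero can be shown to be a mistake. But a deliberate exclusion should be stated, and it would still depart from Protocol Section 9.4.6, which makes no exception.

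The exposure is also not lost. SAP Section 8.2 tabulates concomitant medication by preferred term, with opioids as a category, for each arm. Protocol Section 9.4.3 lists and summarises intra-operative and postoperative opioids, and SAP Section 6.1 provides by-patient listings. This also stands, and it confines the problem to MME. The SAP Section 8.2 table counts users rather than dose, and it uses the mITT Population, whereas safety analyses use the Safety Analysis Population.

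A reader might infer that anyone given one of the six drugs is counted as opioid-free. The formula does not support that: it is true only of patients with no other opioid or, in the daily summary, of days with no other opioid. A patient given sufentanil and then morphine keeps the morphine MME.

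A reader might also infer that the arm comparison is biased. The documents do not show this. The trial is randomised and double-blind, so a site's preference for a drug is not systematically tied to arm, although chance imbalance is possible. A systematic bias would need treatment to affect the use of these six drugs. MME is summarised descriptively with no planned test, and pain and withdrawal scores are reported alongside it.

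**Conclusion.** The point holds in a limited form. Followed as written, the SAP understates the total-opioid-dose endpoint for every patient who receives one of the six drugs, and shows 0 MME for patients or patient-days with no other opioid. It gives no reason, and the result conflicts with the protocol's unqualified statement that recorded doses are converted.

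The count of six in 19 rows and the zero contribution are exact. The size is not known. The 5% to 30% understatement of a group mean rests wholly on an assumed 5% to 30% of exclusive users and equal true MME across patients. If the six drugs are hardly used, the effect is negligible, and the documents are equally compatible with that. The direction of any arm difference cannot be determined. One descriptive safety summary is affected. The primary analysis is not. It is still worth correcting, because the endpoint is named in the protocol and the repair is cheap.

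**What to change.** Before unblinding, revise SAP Table 6 so that each zero is replaced by a non-zero factor taken from one named source, and cite that source.

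Where no factor is accepted for a drug, say so and treat its contribution as not converted rather than as 0:
- Keep the MME computed from any other opioid given that day.
- Flag the patient-day as incomplete. If only unconverted drugs were given, show the MME as not converted, not as 0.
- Report the unconverted drug in its own units by arm, with the number of recipients in the Safety Analysis Population.
- Add a sensitivity summary of MME that excludes flagged patient-days.

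The main summary should not set the whole flagged day to missing. That would discard known MME from other opioids and, under the observed-case rule in SAP Section 6.4, remove mixed-opioid days from the mean. If those are the days of heavier use, the mean would again be too low. For the same reason, the exclusion summary belongs beside the main one as a sensitivity check. On flagged days with other opioids, the retained MME is a lower bound and should be labelled so.

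The cost is a table revision, a footnote and minor programming before database lock. Opioid doses are already recorded in the eCRF, so trial conduct and data collection do not change.

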**Table 6 Conversion Factor**

Opioid Type (Route)	Unit	Conversion Factor
LEVOMETHADONE	mg	8
LEVORPHANOL	mg	7.5
HYDROMORPHONE	mg	4
METHADONE	mg	4
OXYMORPHONE	mg	3
FENTANYL (Topical or Transdermal)	ug/hour	2.4
OXYCODONE	mg	1.5
HYDROCODONE	mg	1
MORPHINE	mg	1
CODEINE	mg	0.15
DIHYDROCODEINE	mg	0.15
FENTANYL (Intravenous, Sublingual or Transmucosal)	ug	0.1
MEPERIDINE	mg	0.1
BUTORPHANOL	mg	0
PENTAZOCINE	mg	0
TAPENTADOL	mg	0
TRAMADOL	mg	0
BUPRENORPHINE	mg	0
SUFENTANIL	mg	0

## 10.9 Analysis for ClinTrial.gov

This section specifies the safety analyses only for ClinTrial.gov, and the summary will not be included in the clinical study report.

The number and proportion of patients who experience TEAEs excluding treatment-related TEAE with an outcome of death and other STEAEs by SOC and PT will be summarized.

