10.3.1 Definition of Serious Adverse Event

If an event is not an AE per the definition above, then it cannot be an SAE even if serious conditions are met.

An SAE is defined as any untoward medical occurrence that, at any dose:	
a. Results in death	
b. Is life threatening	
The term “life threatening” in the definition of “serious” refers to an event in which the patient was at risk of death at the time of the event. It does not refer to an event that hypothetically might have caused death if it were more severe.

c. Requires inpatient hospitalization or prolongation of existing hospitalization	
In general, hospitalization signifies that the patient has been detained (usually involving at least an overnight stay) at the hospital or emergency ward for observation and/or treatment that would not have been appropriate in the physician’s office or outpatient setting. Complications that occur during hospitalization are AEs. If a complication prolongs hospitalization or fulfills any other serious criteria, the event is serious. When in doubt as to whether “hospitalization” occurred or was necessary, the AE should be considered serious.
 
Hospitalization for elective treatment of a preexisting condition that did not worsen from baseline is not considered an AE.

d. Results in persistent disability/incapacity	
• The term disability means a substantial disruption of a person’s ability to conduct normal life functions.• This definition is not intended to include experiences of relatively minor medical significance, such as uncomplicated headache, nausea, vomiting, diarrhea, influenza, and accidental trauma (eg, sprained ankle), which may interfere with or prevent everyday life functions but do not constitute a substantial disruption.
e. Is a congenital anomaly/birth defect	

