- The investigator is obligated to assess the relationship between study treatment and each occurrence of each AE/SAE.
- The relationship of an event to the study treatment will be determined by the investigator or subinvestigator according to the following criteria:
 - Related: An AE that can be reasonably explained as having been caused by the study treatment. For example, the occurrence of the AE can be explained by any of the following: a pharmacological effect of the study treatment (eg, a similar event had been reported previously); an increase/decrease of the dose affects the occurrence or seriousness of the AE; or all other causative factors (eg, medical history, concomitant medication, etc) have been ruled out after careful analysis of sufficient information.

- Not related: An AE that cannot be reasonably explained as having been caused by the study treatment.
- The investigator will use clinical judgment to determine the relationship.
- Alternative causes, such as underlying disease(s), concomitant therapy, and other risk factors, as well as the temporal relationship of the event to study treatment administration will be considered and investigated.
- The investigator will also consult the Investigator's Brochure and/or Product Information, for marketed products, in his/her assessment.
- The investigator should provide a rationale for the causality assessment in the Medical Comment field on the eCRF or if reporting via paper, the rationale for causality should be provided in the narrative section of the paper SAE form.
- There may be situations in which an SAE has occurred and the investigator has minimal information to include in the initial report to the CRO. However, **it is very important that the investigator always make an assessment of causality for every event before the initial transmission of the SAE data to the CRO.**
- The investigator may change his/her opinion of causality in light of follow-up information and send an SAE follow-up report with the updated causality assessment and update the eCRF.

Follow-up of AEs and SAEs

- The investigator is obligated to perform or arrange for the conduct of supplemental measurements and/or evaluations as medically indicated or as requested by the CRO to elucidate the nature and/or causality of the AE or SAE as fully as possible. This may include additional laboratory tests or investigations, histopathological examinations, or consultation with other health care professionals.

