**Table 3** **Definition of Adverse Event Terms**

Term	Definition
TEAE with an outcome of death	TEAE with “Fatal” in terms of outcome
Other STEAE	TEAE with “Serious” in terms of seriousness excluding TEAE with an outcome of death
TEAE leading to discontinuation of the study drug	TEAE with “Drug withdrawn” in terms of the action taken for study drug
Severe TEAE	TEAE with “Severe” in terms of severity
Treatment-related TEAE	TEAE with “Related” in terms of the causal relationship with study drug
Treatment-related TEAE with an outcome of death	Treatment-related TEAE with “Fatal” in terms of outcome
Other treatment-related STEAE	Treatment-related TEAE with “Serious” in terms of seriousness excluding treatment-related TEAE with an outcome of death
Severe treatment-related TEAE	Treatment-related TEAE with “Severe” in terms of severity
Treatment-related TEAE leading to discontinuation of the study drug	Treatment-related TEAE with “Drug withdrawn” in terms of the action taken for study drug

STEAE = serious treatment-emergent adverse event; TEAE = treatment-emergent adverse event.

The number and proportion of patients who experience TEAEs will be summarized by SOC and PT for each treatment group. For these summaries, patients with multiple TEAEs will be counted only once within an SOC and PT. TEAEs with an outcome of death, other STEAE, TEAEs leading to discontinuation of the study drug, treatment-related TEAEs, treatment-related TEAEs with an outcome of death, and other treatment-related STEAEs will be summarized in the same manner.

TEAEs relating to opioid withdrawal defined in Table 4 will also be summarized.

The proportion of specific TEAEs relating to gastrointestinal disorders and opioid withdrawal defined in Table 4 and all TEAEs by severity will be plotted.

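### The exclusions for the registry-only adverse-event table (SAP 10.9) leave in fatal events judged not related, the only serious events it would contain

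*SAP*

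**What the plan says.** SAP Section 10.9 opens by limiting its own reach: "This section specifies the safety analyses only for ClinTrial.gov, and the summary will not be included in the clinical study report". It then asks for the number and proportion of patients with TEAEs, "excluding treatment-related TEAE with an outcome of death and other STEAEs by SOC and PT will be summarized".

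Both exclusions are defined terms in SAP Table 3:

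- *Treatment-related TEAE with an outcome of death*: "Treatment-related TEAE with “Fatal” in terms of outcome". Treatment-related in turn means "TEAE with “Related” in terms of the causal relationship with study drug".
- *Other STEAE*: "TEAE with “Serious” in terms of seriousness excluding TEAE with an outcome of death".

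Table 3 also has a broader term, *TEAE with an outcome of death*, defined without any causality condition: "TEAE with “Fatal” in terms of outcome". Section 10.9 does not use it.

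Two protocol provisions matter as well. The first criterion for a serious adverse event in Section 10.3.1 is "a. Results in death". The causality scale in Section 10.3.2 has two levels, of which the second is "Not related: An AE that cannot be reasonably explained as having been caused by the study treatment". So a fatal event is always serious, and it may be judged not related.

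**The concern.** Table 3 is built from matched pairs. *TEAE with an outcome of death* goes with *Other STEAE*, and the treatment-related version of the first goes with the treatment-related version of the second. Within each pair, the second term removes exactly the deaths that the first term counts, so the two together cover all serious events of that kind.

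Section 10.9 takes the first half of the treatment-related pair and the second half of the general pair. These do not fit together. The general *Other STEAE* drops all deaths, while the treatment-related death term puts only some of them back into the excluded set. Deaths judged not related fall through the gap.

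What is at stake is one public table. A programmer who follows the defined terms would tabulate unrelated fatal events by system organ class and preferred term, alongside events that are not serious. Because the summary stays out of the clinical study report, review of that report would not show the error.

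**Working it through.** No figure in the plan is in question, so the check is one of classification.

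**Inputs.** Each TEAE has three attributes: serious (S), fatal (F) and related (R). Protocol 10.3.1 makes every fatal event serious, so F implies S. That leaves six possible classes.

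**Rule as written (SAP 10.9 with Table 3).**

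- Excluded set = (F and R) or (S and not F).
- Retained set = everything else = (F and not R) or (not S).

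**Rule without the word 'treatment-related'.**

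- Excluded set = F or (S and not F) = S.
- Retained set = not S.

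**A second grammatical reading.** 'Treatment-related' could be taken to govern both exclusions. The excluded set is then R and (F or (S and not F)) = R and S.

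| Class of TEAE | As written | 'Treatment-related' governs both | 'Treatment-related' deleted |
|---|---|---|---|
| Fatal, related | removed | removed | removed |
| Fatal, not related | **kept** | **kept** | removed |
| Serious non-fatal, related | removed | removed | removed |
| Serious non-fatal, not related | removed | **kept** | removed |
| Non-serious, related | kept | kept | kept |
| Non-serious, not related | kept | kept | kept |

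**Result.** As written, the rule removes three of the four serious classes; the one it leaves is unrelated deaths. The second reading removes only two of the four and also lets in unrelated non-fatal serious events. With the word deleted, all four serious classes are removed and only the two non-serious classes remain.

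**Comparison with SAP 10.1.** That section summarises all TEAEs with a fatal outcome, with no causality condition, and other STEAEs as a separate category. It does so overall and by system organ class and preferred term. The treatment-related versions are listed in addition. There the pairs are matched, so no serious event is missed.

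**The case against.** The strongest reply is that the intention is plain and the consequence small. The stray word looks like a copying slip, since 10.1 uses the matched pairs. If 'other STEAEs' is read in its everyday sense, as all remaining serious events, unrelated deaths are removed after all. The table mock-ups are in separate shells that are not part of these documents and may show the intended content. Section 10.9 never calls the table non-serious. No death is lost either: 10.1 counts them all, and protocol Section 9.4.6 has every adverse event listed.

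Much of this stands. The non-serious label is an inference from what the exclusions leave behind, and the point should be put no more strongly than that. The wording probably is a slip. The study-report output is sound. What does not stand is the everyday reading of 'other STEAEs': Table 3 defines the term, and the definition takes out every fatal event. Shells that showed something different would conflict with the SAP text; they would not correct it.

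A reader might go further and infer that the trial's reporting of deaths is unreliable, or that unrelated deaths would be missing from the registry record. The documents support neither. The events are placed in a table where they do not belong, not dropped, and 10.9 does not describe what else would be posted.

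**Conclusion.** The exclusion rule is wrong as written, with a narrow effect. Every patient with a fatal TEAE judged not related would be counted for that event in a table from which all other serious TEAEs have been removed. This rests on the Table 3 definitions and on the protocol rule that death makes an event serious; it needs no numerical assumption.

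The number of patients affected is the number with such an event, and it is zero if there are none. A reader might want to put a figure on it by applying a surgical mortality rate to the 200 to 340 planned patients, or might suppose that most deaths after bowel surgery would be judged unrelated. Neither document gives a mortality rate or a share judged unrelated. Any such count would need both as assumptions, and it would also have to use the Safety Analysis Population (all dosed patients) in place of all randomised patients. No estimate is offered here.

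The effect stops at the registry posting. No efficacy result, and no safety result in the study report, changes. This is a minor correction, worth making because the table is public.

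**What to change.** In SAP Section 10.9, delete 'treatment-related' from the first exclusion. The table then excludes TEAEs with an outcome of death and other STEAEs, both as Table 3 already defines them, and so removes every serious TEAE. It would also help to state in 10.9 that the table is meant to show non-serious TEAEs, if that is the intention, and to check that the corresponding table shell agrees.

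The cost is one word in the SAP, plus an optional clarifying phrase. It needs no new data, no protocol amendment and no change to any other analysis, and it can be made before database lock.
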